12 ADVERSE EVENT REPORTING

12.1 Definitions

12.1.1 Adverse Event

For the purposes of this trial, an AE is defined as follows:

Any new unfavorable/unintended signs/symptoms (including abnormal laboratory findings when relevant) or diagnosis or worsening of a preexisting condition that occurs following Screening (Visit 1) and at any point up to the posttreatment Safety Follow-up Visit (Visit 10), which may or may not be considered to be related to the IMP. Any event that is the result of a trial procedure must be recorded as an AE.

Surgical/investigational procedures are not AEs. The medical reason for the procedure is the AE. Elective hospitalizations for pretrial existing conditions or elective procedures are not AEs. An exception may be if the patient has an AE during hospitalization that prolongs his or her scheduled hospital stay, in which case it would be considered a SAE (refer to [Section 12.2](#)).

If reporting a fatal event, the SAE term should be the underlying cause of the death (e.g., disease or medical condition leading to death).

12.1.2 Investigator

The term investigator refers to the trial PI or a formally delegated trial physician.

12.2 Serious Adverse Events

During clinical investigations, AEs may occur that, if suspected to be IMP related, might be significant enough to lead to important changes in the way the IMP is developed (e.g., change in dose, population, monitoring need, or consent forms). This is particularly true for events that threaten life or function. Such SAEs will be reported promptly to regulatory authorities, applicable IRBs/IECs, and investigators (expedited reporting) by GW.

An AE must only be classed as serious, i.e., an SAE, when the event falls into one of the following criteria:

- Results in death
- Is life-threatening*
- Requires inpatient hospitalization or prolongation of existing hospitalization

- Results in persistent or significant disability/incapacity
- Is a congenital anomaly/birth defect
- Is medically significant**

*The term “life-threatening” in the definition of “serious” refers to an event in which the patient was at risk of death at the time of the event; it does not refer to an event that, hypothetically, might have caused death if it were more severe.

**Medical and scientific judgment should be exercised in deciding whether SAE reporting is appropriate in other situations. Important medical events may not be immediately life-threatening or result in death or hospitalization but may jeopardize the patient or may require intervention to prevent one of the other outcomes listed in the definition above. These should also usually be considered serious. Examples of such events are intensive treatment in an emergency room or at home for allergic bronchospasm, blood dyscrasias or convulsions that do not result in hospitalization, development of drug dependency or drug abuse, or positive COVID test.

12.3 Reporting Procedures for Serious Adverse Events

All SAEs occurring during the trial must be reported to GW with any other supporting information and recorded in the AE section of the eCRF. Any ongoing SAEs should be followed up until resolution wherever possible. For all deaths, the working diagnosis or cause of death as stated on a death certificate, available autopsy reports, and relevant medical reports should be sent to GW promptly.

All SAEs must be recorded in the eCRF within 24 hours of discovery or notification of the event. The GW Pharmacovigilance Department (PWD) will be automatically notified that an SAE has been recorded. Any additional information required for a case (follow-up or corrections to the original case) will be requested by GW PVD through eCRF queries.

The investigator is not obliged to actively monitor for any new SAEs that occurred after the last formal Safety Follow-up Visit (Visit 10). However, if the investigator becomes aware of any deaths or a new IMP-related SAE occurring within 28 days of the final dose of IMP, these should be reported to the GW PVD.

Any other problem discovered after Visit 10 that is deemed to be an unexpected safety issue and is likely to have an impact on patients who have taken part in the trial must be treated as an SAE and reported to the GW PVD. Such posttrial SAEs do not need to be

recorded on the patient's eCRF if editing rights to the eCRF have been removed due to final trial database lock. GW PVD may request safety follow-up information after the final trial visit in order to investigate a potential safety issue.

Contact details for the GW PVD are provided at the front of the site files for all trial site and upon completion of the GW SAE report form.

12.4 Pregnancy

Any patient, or patient's partner, who has become pregnant while receiving the IMP, or within 3 months of the last dose of IMP, must be reported to the GW PVD. Where possible, the investigator should provide the outcome of the pregnancy.

All pregnancies must be recorded in the eCRF within 24 hours of awareness. The GW PVD will be automatically notified that a pregnancy has been recorded. Any additional information required for a case (follow-up or corrections to the original case) will be requested by GW PVD through eCRF queries.

The investigator is not obliged to actively monitor for any pregnancies that commence more than 3 months after the final dose of IMP. However, if the investigator becomes aware of a new pregnancy outside this time limit, then he/she should report it as above. The GW PVD will follow up for all pregnancy outcomes.

12.5 Causality Assessment

Causality assessment is required for all AEs and SAEs. Causality assessment must only be assigned by the investigator. All cases judged as having a reasonable suspected causal relationship to the IMP must be reported as such. The expression "*reasonable causal relationship*" is meant to convey in general that there are facts (evidence) or arguments to suggest a causal relationship.

The following question, which must be answered by the investigator for all AEs, is used to capture the reasonable causal relationship of an event to the IMP:

"In your opinion, is there a plausible relationship to the IMP?" The answer is either "yes" or "no."

Events that start before the first dose of IMP (pretreatment) should be considered as not causally related. Where a pretreatment event worsens in severity following the first dose of IMP, a new event record should be entered into the eCRF.

Considering the explanation given above, investigators are strongly encouraged to express their opinion on what the cause of an AE might be. For individual patients, the investigator is usually in the best position to assess the underlying suspected cause of an AE. For all AEs and especially SAEs, it is important that the investigator assess not only the possible role of the IMP but also other potential contributing factors. Factors for consideration of the underlying cause may include the following:

- Medical and disease history
- Lack of efficacy/worsening of treated condition
- Concomitant or previous treatment
- Withdrawal of IMP
- Protocol-related procedure

12.6 Reporting Procedures for All Adverse Events

All AEs (including SAEs) occurring during the trial will be reported on the running logs in the AE section of the eCRF. This includes all events from the time following Screening (Visit 1) up to and including the Safety Follow-up Visit (Visit 10), whether or not attributed to IMP and observed by the investigator or patient.

The following information will need to be provided for all AEs:

A) Adverse Event (Diagnosis or Syndrome if Known or Signs and Symptoms)

Where the investigator cannot determine a diagnosis, signs or symptoms should be recorded in the AE section of the eCRF. Once a diagnosis has been determined, the AE section of the eCRF must be updated to reflect the diagnosis in replacement of the original symptoms. In circumstances where only a provisional diagnosis is possible (working diagnosis), the eCRF must be updated to reflect the provisional diagnosis in replacement of the original symptoms. In some circumstances, it may be relevant for the investigator to include the symptoms alongside the diagnosis in the verbatim event description. However, the diagnosis (full or provisional) should be clearly stated, e.g., symptom due to disease (i.e., weakness due to cancer, tremor due to MS, headache and fever due to pneumonia, and generalized weakness due to hepatic cancer progression).

B) Adverse Event Start Date and Stop Date

The start and stop dates of the event must be provided. All AEs require these fields to be completed in full. Partial dates or missing dates are not normally acceptable, and

significant effort must be undertaken to obtain any unknown information. If a precise date is not known, an estimated date should be provided instead. When a complete date cannot be given, much information as possible (i.e., month and year or, in exceptional circumstances, just year) should be recorded. When the actual start date becomes known, the eCRF must be updated to replace the previously recorded date.

C) Outcome

The outcome of the event must be recorded accurately and classified into one of the following categories:

- Recovered/Resolved
- Recovered/Resolved with Sequelae
- Not Recovered/Not Resolved
- Fatal

D) Severity

When describing the severity of an AE, the terms mild, moderate, or severe should be used. Clinical judgment should be used when determining which severity applies to any AE.

If the severity of an AE fluctuates day-to-day, e.g., a headache or constipation, the change in severity should not be recorded each time; instead, only the worst observed severity should be recorded with AE start and stop dates relating to the overall event duration, regardless of severity.

A severe AE is not the same as an SAE. For example, a patient may have severe vomiting, but the event does not result in any of the SAE criteria above. Therefore, it should not be classified as serious.

E) Causality

See [Section 12.5](#) above.

F) Action Taken with Trial Medication

This question refers to the action taken with the IMP due to an AE. The action with the IMP must be classed as follows:

- Dose Not Changed
- Dose Reduced
- Drug Interrupted
- Drug Withdrawn

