10.21 Adverse Events

10.21.1 Start and Stop Date Imputation

Table 10.21-1 Imputation Rules for Partial Adverse Events Start/Stop Dates

Parameter	Missing	Additional Conditions	Imputation
Start date for AEs	D	M and Y same as M and Y of first dose of study drug	Date of first dose of study drug
		M and/or Y not same as date of first dose of study drug	First day of month but should fall after 1st study drug intake or if impossible after informed consent date
	D and M	Y same as Y of first dose of study drug intake during period 1 and 2	Date of first dose of study drug
		Y after Y of first dose of study intake during Period 1 but same Y as 1 st study drug intake during Period 2	Date of first drug intake during period 2
		Y prior to Y of first dose of study drug but same as Y of informed consent date	Date of informed consent
		Y after Y of last study drug intake	The earliest date between date of last study drug intake + 14 days and end of study date
	D, M, Y	Not allowed by the system	Not applicable
Stop date for AEs	D	M and Y same as M and Y of last dose of study drug	The earliest date between date of last dose of study drug and end of study date
		M and/or Y not same as date of last dose of study drug	The earliest date between last day of month and end of study date
	D and M	Not allowed by the system	Not applicable
	D, M, Y	Not allowed by the system	Not applicable

AE = Adverse events; D = day; M = month; Y = year

Note: In all cases, if an estimated start date is after a complete stop date, use the first day of the stop date month.

Similarly, if the estimated stop date is before a complete or imputed start date, use the last day of the start date month.

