12.7.1 Adverse Events

Adverse events (AEs) will be coded using MedDRA 24.0 or higher according to the version in use at time of database lock. All safety analyses of AEs will be performed by actual treatment arm and reported using the Safety Analysis Set. An AE will be considered a TEAE if it first occurs or worsens in severity or seriousness after the first dose of IMP intake and before the last dose date + 15 days.

All AEs will be classified during the pre-treatment period, the 51-day safety on-treatment period or during the follow-up period as follows:

- Events that occurred before first IMP intake without worsening or becoming serious after the first IMP dose are classified as **pre-treatment AEs**;
- Events that occurred or worsens between first IMP dose and 14 days after IMP last dose are classified as on-treatment AE and are defined as **treatment-emergent AEs** (TEAEs);
 - TEAE occurring during 21-day on-treatment safety Period 1 will be considered emergent to actual treatment received during Period 1 (as defined in [Section 10.1.1](#)).
 - TEAE occurring during 21-day on-treatment safety Period 2 will be considered emergent to actual treatment received during Period 2 (as defined in [Section 10.1.1](#)).
- Events occurring more than 15 days after last dose are classified as **follow-up AEs**.

Consequently, TEAEs will be summarized by treatment arm using the actual treatment received at each given period. Any adverse event occurring during the wash-out period will be linked to the actual treatment arm defined for Period 1, whereas any AEs occurring after last IMP dose will be linked to the actual arm defined at time of permanent study drug discontinuation.

The following events will not be identified as AEs in this study:

- Medical or surgical procedures (e.g., surgery, endoscopy, tooth extraction, etc.). The condition (the “triggering event”) that leads to the procedure are adverse events and will be reported as such.
- Pre-existing conditions present or detected prior to the first dose of study drug that do not worsen during the study.

Counting rules

For incidence reporting, if a patient reported more than one AE that was coded to the same preferred term/system organ class within a given treatment arm, the patient will be counted only once for that specific preferred term/system organ class by treatment arm and the rules defined below will be applied.

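### Two adverse event rules ignore the start of Period 2, so an event that worsens, or begins with a partial date, after the first Period 2 dose can be credited to the Period 1 treatment

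*Protocol*

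**What the plan says.** **Recording.** Protocol 12.6 D opens with its condition, "If the severity of an AE fluctuates day-to-day, e.g., a headache or constipation", and then says that "only the worst observed severity should be recorded with AE start and stop dates relating to the overall event duration, regardless of severity". Protocol 12.5 is the only explicit instruction to open a second record: "Where a pretreatment event worsens in severity following the first dose of IMP, a new event record should be entered into the eCRF". No counterpart is given for the first dose of Period 2.

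**Attribution.** SAP 12.7.1 defines treatment emergence from the first dose in the trial: "An AE will be considered a TEAE if it first occurs or worsens in severity or seriousness after the first dose of IMP intake". It then assigns events by period: "TEAE occurring during 21-day on-treatment safety Period 1 will be considered emergent to actual treatment received during Period 1", and likewise "TEAE occurring during 21-day on-treatment safety Period 2 will be considered emergent to actual treatment received during Period 2". Events in the washout go to the Period 1 treatment. How to attribute a Period 1 event that worsens in Period 2 is not stated.

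**Partial dates.** Protocol 12.6 B wants full dates ("All AEs require these fields to be completed in full") and asks for an estimated date when the exact one is unknown. It still allows a partial date as a last resort. SAP Table 10.21-1 covers that case. If only the day is missing, the start becomes the first-dose date when the month is the same. Otherwise it becomes "First day of month but should fall after 1st study drug intake or if impossible after informed consent date". A year-only start becomes the first-dose date when both periods fall in that year. A separate row uses the first Period 2 dose when the year has turned. SAP 12.7.1 feeds the imputed dates into the TEAE tables.

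**The concern.** In a crossover the first Period 2 dose is a second start of treatment, and an event must be placed before or after it to be credited to the right product. The recording rule looks back only to the first dose in the trial. The imputation rule is bounded only by that dose or by consent.

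TEAE frequency is a secondary endpoint. The SAP tabulates it by treatment, maximum severity, relatedness and action taken, and analyses time to first event of special interest by treatment. One record that spans both periods carries one severity, one causality answer and one action taken, so it cannot supply a worst severity for each treatment. The trial has no data safety monitoring committee (Protocol 14), so these tables carry much of the tolerability comparison.

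**Working it through.** The plan gives no figure on this point to reproduce.

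**1. Recording rule.** Take a headache that fluctuates, starts on placebo in Period 1, persists through washout and is worst on nabiximols in Period 2. Protocol 12.6 D gives one record with the Period 1 start date and the worst severity. Protocol 12.5 does not ask for a second record, because the event is not pretreatment. SAP 12.7.1 counts worsening, but no worsening date exists. The start date is the only date left, and it points to placebo. This is an inference, since the SAP does not address the case.

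Size per patient, with 68 completers (SAP 8.2) as an approximate denominator; SAP 12.7.1 actually uses patients with at least one spray of that treatment:
- Any-TEAE incidence: the placebo count is right, because the event did begin there. The nabiximols count is missing, so nabiximols loses 1/68 = 1.47 points.
- Severity-specific tables: the severe category also gains 1/68 on placebo, so the difference moves by 2/68 = 2.94 points.
- With 46 completers (Protocol 13.1): 1/46 = 2.17 and 2/46 = 4.35 points.

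**2. Day-missing start.** Period 2 starts on Day 31 (Protocol 9.1.4.1). I read first dose of study drug as the first dose in the trial, as in SAP 10.1.2. Assume onset uniform over Days 31-51 and Day 1 equally likely on any of 365 dates.
- Example: Day 1 on 10 September, first Period 2 dose on 10 October, true onset 15 October. The imputed start is 1 October, which is Day 22, in washout, so the event is booked to Period 1.
- General: the imputed date is late enough only if the first of a month falls between the Period 2 dose and the onset, inclusive. For onset k days after the dose (k = 0 to 20), that holds for 12(k + 1) of 365 start dates.
- Correctly placed: 12 × (1 + 2 + … + 21) / (365 × 21) = 12 × 231 / 7,665 = 36.2%. Booked to Period 1: 63.8%. Direct enumeration gives the same.
- With onset over Days 31-65 (14 days more): 42%.
- Reverse error, for onset on Days 1-30: 0%, because the rule never imputes later than the true onset.

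**3. Year-only start.** Onset on Days 31-51 lies 30 to 50 days after Day 1, mean 40. It falls in the Day 1 year for (365 − 40)/365 = 89% of cases, and all of these go to Period 1. The year-crossing row handles 30/365 = 8% correctly, and 10/365 = 3% match no row. The reverse error, through the year-crossing row, is 14.5/365 = 4%.

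**4. Net effect.** Let λN and λP be events per patient-period, with balanced sequences and a common share f of Period 2 events moved to Period 1.
- Recorded nabiximols rate: [λN(2 − f) + fλP]/2. Recorded placebo rate: [λP(2 − f) + fλN]/2.
- Recorded difference: (1 − f)(λN − λP).
- With assumed rates 0.60 and 0.30 (true difference 0.300), f = 2%, 5%, 10% and 20% gives 0.294, 0.285, 0.270 and 0.240.
- At f = 10% and 34 patients per sequence, 34 × 0.10 × 0.60 = 2.0 nabiximols events go to placebo, and 34 × 0.10 × 0.30 = 1.0 placebo event goes to nabiximols.

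Neither the rates nor f are in the documents.

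**The case against.** Much of the case on the other side stands.
- Protocol 12.6 D is aimed at daily ups and downs. A sustained step-up, a new event or a recurrence after resolution is not governed by it. Protocol 12.1.1 counts worsening of a preexisting condition as an adverse event at any point up to Visit 10, which gives a site grounds to open a new record. Completion guidance for the eCRF is not among the documents. But nothing requires the new record at Period 2, so practice may vary by site.
- Partial dates should be rare. Full or estimated dates are required, and events are reviewed at visits or calls on Days 8, 15, 21, 31, 38, 45 and 51, at most 10 days apart. The 64% applies only to Period 2 onsets with a missing start day.
- TEAE summaries are descriptive, and listings show the actual dates.

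A reader might infer that the rules hide nabiximols harms under placebo. The documents do not support that as the overall effect: in the nabiximols-first sequence the same rules credit placebo-period events to nabiximols. The one-way finding for day-missing dates concerns periods, not treatments. Nor are Period 2 events in general charged to Period 1, since a complete start date places them correctly. Nor does a 2.9-point swing apply to any-TEAE incidence under the recording rule.

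**Conclusion.** Both gaps are real and worth closing before database lock. The recording gap concerns fluctuating events that span the start of Period 2, and its effect on attribution is inferred from the SAP's silence. The imputation gap is a stated rule that misplaces 64% of Period 2 onsets with a missing start day and, where both first doses and the onset fall in one calendar year, every year-only Period 2 onset.

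The expected net effect is attenuation of the treatment difference in TEAEs. That rests on balanced sequences and a similar share of affected events in each. The total size cannot be fixed, because the documents give no count of partial-date or spanning events. It may be small. The case for acting is that a crossover safety table should not depend on a rule that overlooks the second treatment start, and that the correction is cheap.

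**What to change.** **Protocol 12.5 and 12.6 D.** Extend the new-record rule to any event ongoing at the first Period 2 dose that worsens in severity or seriousness afterwards, with its own start date, severity, causality and action taken. Limit the single-record rule to one treatment period. State in SAP 12.7.1 that the new record is emergent to the Period 2 treatment. For records already entered, query sites about events ongoing at Visit 6 before database lock.

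**SAP Table 10.21-1.** Add a row for partial start dates compatible with Period 2, using the Visit 6 predose adverse event review and the stop date:
- event not present at Visit 6 predose: impute the first Period 2 dose date;
- event present: keep Period 1;
- unresolved: report the TEAE tables under both attributions. Defaulting to nabiximols would build in a directional bias.

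**Cost.** A sentence or two in the protocol and the eCRF guidance, one SAP row with a matching line in 12.7.1, a few more event records, some site queries where the log does not show Visit 6 status, and one small sensitivity table.

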12.7 Follow-up Procedures for Adverse Events

The investigator may be asked to provide follow-up information to the GW PVD for any AEs reported or during the investigation of potential safety issues. Such requests for additional safety information may occur after Visit 10, after the trial.

AEs considered related to the IMP by the investigator or the sponsor should be followed up until resolution or the event is considered stable.

It will be left to the investigator's clinical judgment whether or not an AE is of sufficient severity to require the patient's withdrawal from treatment. A patient may also voluntarily withdraw from treatment due to what he or she perceives as an intolerable AE. Further details of withdrawal are presented in [Section 10](#). If either of these occurs, the patient must undergo an end-of-treatment assessment and be given appropriate care under medical supervision until symptoms cease or the condition becomes stable. If a safety concern is identified following withdrawal of a patient, GW may contact the investigator for additional follow-up information.

